#### LIST OF ABBREVIATIONS

Abbreviations pertain to the statistical analysis plan (SAP) only (not the tables, figures, and listings [TFLs]).

ADaM analysis data model

AE adverse event

AUC area under the plasma concentration-time curve

 $AUC_{0-\infty}$  area under the plasma concentration-time curve from time 0 extrapolated to

infinity

AUC0-tlast area under the plasma concentration-time curve from time 0 to the time of

last quantifiable plasma concentration (tlast)

 $AUC_{0-\tau}$  area under the plasma concentration-time curve calculated over the dosing

interval (τ)

BLQ below the limit of quantification

CDISC Clinical Data Interchange Standards Consortium

Cmax maximum observed plasma concentration Cmin minimum observed plasma concentration

CRU Clinical Research Unit
CSR clinical study report
DN dose normalized
ECG electrocardiogram

Emax maximum pain intensity ICF informed consent form

ICH International Council for/Conference on Harmonisation of Technical

Requirements for Registration of Pharmaceuticals for Human Use

LLOQ lower limit of quantification

MedDRA Medical Dictionary for Regulatory Activities

NC not calculated NR no result

PD pharmacodynamic(s) PK pharmacokinetic(s)

QTc QT interval corrected for heart rate

QTcB QT interval corrected for heart rate using Bazett's formula
QTcF QT interval corrected for heart rate using Fridericia's formula

R^2-adj adjusted coefficient for determination of exponential fit

 $RAAUC_{0-\tau}$  observed accumulation ratio based on  $AUC_{0-\tau}$   $RAC_{max}$  observed accumulation ratio based on  $C_{max}$ 

SAP statistical analysis plan

SC subcutaneous
SD standard deviation

 $t_{1/2}$  apparent plasma terminal elimination half-life

TCP temporal change parameter

TEAE treatment-emergent adverse event  $tE_{max}$  time of maximum pain intensity

TFL table, figure, and listing

tmax time of maximum observed plasma concentration

WHODrug World Health Organization Drug Dictionary

%AUCextrap percentage of AUC that is due to extrapolation from the last measurable

plasma concentration to infinity

#### 1. INTRODUCTION

This SAP has been developed after review of the clinical study protocol (Final Version 5 dated 27 September 2019) and electronic case report form.

This SAP describes the planned analysis of the pharmacokinetic (PK), pharmacodynamic (PD), and safety and tolerability data from this study. A detailed description of the planned TFLs to be presented in the clinical study report (CSR) is provided in the accompanying TFL shells document.

In general, the analyses are based on information from the protocol, unless they have been modified by agreement with OliPass Corporation. A limited amount of information about this study (eg, objectives, study design) is given to help the reader's interpretation. This SAP must be finalized prior to the lock of the clinical database for this study. When the SAP and TFL shells are approved, they will serve as the template for this study's CSR.

This SAP supersedes any statistical considerations identified in the protocol; where considerations are substantially different, they will be so identified. If additional analyses are required to supplement the planned analyses described in this SAP, they may be performed and will be identified accordingly in the CSR. Any substantial deviations from this SAP will be agreed with OliPass Corporation and identified in the CSR.

This SAP is written with consideration of the recommendations outlined in the International Conference on Harmonisation (ICH) E9 guideline *Statistical Principles for Clinical Trials* and ICH E3 guideline *Structure and Content of Clinical Study Reports*. 

The document history is presented in Appendix 1.

#### 2. STUDY OBJECTIVES

The primary objective of the study is to assess the safety and tolerability of single and multiple subcutaneous (SC) doses of OLP-1002 in healthy subjects.

The exploratory objectives of the study are to evaluate the PD effect of OLP-1002 following single SC doses in healthy volunteers using a capsaicin pain model, and to monitor the effects of single SC doses of OLP-1002 on cardiac QT interval. Where possible, single and/or multiple subcutaneous dose PK of OLP-1002 in healthy subjects will be determined.

#### 3. STUDY ENDPOINTS

## 3.1. Primary Endpoints

The primary safety endpoints for this study are as follows:

- incidence and severity of adverse events (AEs)
- vital signs measurements (blood pressure, pulse rate, respiratory rate)
- 12-lead electrocardiogram (ECG) parameters

• incidence of clinical laboratory abnormalities, based on clinical chemistry, hematology, and urinalysis test results

- physical examinations
- injection site assessment
- demonstrate that exposure to OLP-1002 does not exceed pre-defined exposure limits from non-clinical studies.

## 3.2. Exploratory Endpoints

The following exploratory objectives will be assessed:

- pain intensity and duration will be assessed by area under the curve (AUC), maximum pain intensity (Emax), and time of maximum pain intensity (tEmax), calculated using a capsaicin-evoked pain model. The exploratory endpoint of secondary hyperalgesia will be assessed by the area of secondary area of hyperalgesia (Part A only).
- continuous (24-hour) ECG monitoring will be recorded in this study and archived for potential future analysis of OLP-1002 effects on the QT interval (Part A only).
- heat pain threshold measurements and heat pain tolerance measurements.
- For Part A, the single ascending dose, PK outcome endpoints of OLP-1002 are as follows:

## Primary PK

- o area under the plasma concentration-time curve (AUC) from time 0 to infinity  $(AUC_{0-\infty})$  (actual and dose normalized [DN])
- AUC from time 0 to the time of the last quantifiable concentration (AUC0-tlast) (actual and DN)
- o maximum observed plasma concentration (Cmax) (actual and DN)

#### Secondary PK

- $\circ$  time of the maximum observed plasma concentration ( $t_{max}$ )
- $\circ$  apparent plasma terminal elimination half-life ( $t_{1/2}$ )
- For Part B, the multiple ascending dose PK outcome endpoints of OLP-1002 are as follows:

## Primary PK

- o AUC over a dosing interval (AUC0- $\tau$ ) (actual and DN)
- o AUC0-∞ (actual and DN)

**CONFIDENTIAL** 

**SAP** Covance Study: 8379789 Protocol Reference: OLP-1002-001

o Cmax (actual and DN)

## Secondary PK

- o minimum observed plasma concentration (Cmin)
- $\circ$   $t_{max}$
- $0 t_{1/2}$
- o observed accumulation ratio based on AUC0- $\tau$  (RAAUC0- $\tau$ )
- o observed accumulation ratio based on Cmax (RACmax).
- o Temporal change parameter (TCP)

Other PK parameters may also be added if deemed necessary.

#### 4. STUDY DESIGN

This will be a double-blind, randomized, placebo-controlled, single and multiple SC dose study conducted in 2 parts.

#### 4.1. Part A

Part A will comprise a single-dose, sequential-group design. Overall, 68 healthy subjects will be studied in 11 groups.

Potential subjects will be screened to assess their eligibility to enter the study within 28 days prior to the first dose administration. Potential subjects for Groups A2, A4, A6, A9, A10, and All will attend a pre-screening visit for an intradermal capsaicin test.

Each subject will participate in 1 treatment period only, and will reside at the Clinical Research Unit (CRU) from Day -2 (2 days before dosing) to Day 3. All subjects will return for non-residential visits on Days 4, 7 (±2 days), 10 (±2 days), and 14 (±2 days), and for a poststudy visit on Day 28 (±2 days).

Based on the ongoing review of the safety and tolerability, additional non-residential visits may be required. The number of additional visits per subject will not exceed 3 and will not extend beyond Day 28 (±2 days).

Doses will be administered in an escalating manner following satisfactory review of safety and tolerability data up to Day 10 (216 hours postdose) from the lower dose levels. For doses ≥12 µg, PK data will also be reviewed up to Day 7 prior to dose escalation.

In Part A, Groups A1, A3, A5, A7, and A8 will consist of 4 subjects; 3 subjects will receive OLP-1002 and 1 subject will receive placebo. To assess PD parameters, Groups A2, A4, A6, A9, A10, and A11 will consist of 8 subjects; 6 subjects will receive OLP-1002 and 2 subjects will receive placebo.

Sentinel dosing will be employed for all groups in Part A. To maintain the blind in a 4-subject group, the first subject will be dosed 48 hours before the second subject, and the second subject will be dosed 48 hours prior to the third and fourth subjects. In PD assessment groups, 2 subjects (1 active: 1 placebo) will be dosed 48 hours before the remaining 6 subjects (5 active: 1 placebo).

The total duration of study participation for each subject (from Screening through Follow-up visit) is anticipated to be approximately 8 weeks.

A schematic of the study design is presented in Figure 1.

Figure 1: Study Design (Part A)

Active = OLP-1002; SC = subcutaneous 6 groups consist of 8 subjects (6 active: 2 placebo); all other groups will consist of 4 subjects (3 active: 1 placebo).

#### **4.2. Part B**

Part B will comprise a multiple-dose, sequential-group study. Overall, 32 subjects will be studied in 4 groups (Groups B1 to B4), with each group consisting of 8 subjects. Up to 2 additional groups (16 subjects in total) may be included for further assessment of safety and tolerability.

Potential subjects will be screened to assess their eligibility to enter the study within 28 days prior to the first dose administration. Each subject will participate in 1 treatment period only and reside at the CRU from Day -1 until Day 15.

All subjects will return for non-residential visits on Days 18 ( $\pm 2$  days), 22 ( $\pm 2$  days), 25 ( $\pm 2$  days), and 29 ( $\pm 2$  days), and for a poststudy visit on Day 57 ( $\pm 2$  days).

In each of Groups B1 to B4, 6 subjects will receive OLP-1002 and 2 subjects will receive placebo. For all subjects, a single SC dose will be administered on Days 1, 4, 7, 10, and 13. Prior to each dosing occasion a physician will review the available safety and tolerability data from each subject to confirm it is acceptable to continue dosing. The dosing frequency in Part B may be changed following review of data from groups in Part A.

Sentinel dosing will only occur in Part B at dose levels where exposure to OLP-1002 at steady state is predicted to exceed exposures that have been shown to be safe and well

Covance Study: 8379789

[figure not shown]
tolerated in earlier groups in Parts A or B. In the event of sentinel dosing, 2 subjects (1 active, 1 placebo) will be dosed at least 4 days prior to the remaining 6 subjects (5 active: 1 placebo). Safety data for the sentinel subjects from at least 2 additional doses will be reviewed prior to dosing the remaining subjects (i.e. sentinel subjects' safety data after doses 1 and 2 will be reviewed prior to the remaining subjects receiving dose 1). In addition, safety data from each subject will be reviewed by a physician prior to each dose to approve continued dosing.

Doses will be administered in an escalating manner following satisfactory review of safety, tolerability, and PK data up to Day 22 (216 hours post-final dose) from the lower dose levels. Part B may start after a review of the safety, tolerability, and available PK for Groups A1 to A6. The total daily dose administered will not exceed the highest single dose given in Part A.

The total duration of study participation for each subject (from Screening through Follow-up visit) is anticipated to be approximately 12 weeks.

A schematic of the study design is presented in Figure 2.

Figure 2: **Study Design (Part B)** 

Active = OLP-1002; SC = subcutaneous; TBC = to be confirmed. All doses will be confirmed based on results of Part A and previous groups in Part B Groups B5 and B6 will be included if required.

#### 5. SAMPLE SIZE JUSTIFICATION

No formal statistical assessment, in terms of sample size, has been conducted as this is the first time OLP-1002 is being administered to humans. However, the number of subjects in each part of the present study is common in early clinical pharmacology studies and is considered sufficient to achieve the objectives of the study. As part of Protocol Version 5, 3 additional groups will be included in Part A (Groups A9, A10, and A11) and 1 additional group will be included in Part B (Group B4). Up to 2 additional groups of 8 subjects may be added to Part B (6 active; 2 placebo).

#### 6. STUDY TREATMENTS

#### **6.1. Part A**

The study treatment names and ordering to be used in the TFLs are presented in Table 1.

**Table 1: Presentation of Study Treatments in TFLs (Part A)** 

Group	Study Treatment	Order in TFLs
A1 to A11	Placebo a	1
A1	30 ng OLP-1002	2
A2	120 ng OLP-1002	3
A3	400 ng OLP-1002	4
A4	1.2 μg OLP-1002	5
A5	3 μg OLP-1002	6
A6	6 μg OLP-1002	7
A7	12 μg OLP-1002	8
A8	20 μg OLP-1002	9
$A9^b$	40 μg OLP-1002	10
$A10^{b}$	80 μg OLP-1002	11
A11 b	160 μg OLP-1002	12

<sup>a Placebo will be pooled across all groups

All treatments described above are the planned treatments. The TFLs will reflect the actual treatments received, and dose levels will be displayed in increasing order.

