## 8.6. Pharmacodynamic Assessments (Part A Only)

Capsaicin intradermal test will be performed for subjects in Groups A2, A4, A6, A9, A10 and A11. Each subject will be tested at a pre-screening visit before being tested twice during the study (1 predose and 1 postdose).

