## 8.7. Safety and Tolerability Assessments

#### 8.7.1. Adverse Events

All AEs will be coded using the Medical Dictionary for Regulatory Activities (MedDRA) Version 22.0 (or higher if upversioned during the study).

A treatment-emergent adverse event (TEAE) will be defined as an AE that starts during or after dosing (Part A) or the first dose (Part B), or starts prior to dosing (Part A) or the first dose (Part B) and increases in severity after dosing (Part A) or the first dose (Part B).

A treatment-related TEAE will be defined as a TEAE with a relationship of possibly related or related to the study treatment, as determined by the investigator.

All AEs will be listed. In addition to the data recorded in the database, the listings will include derived onset time and duration. Onset time will be calculated from the time of dosing TEAEs only.

The frequency of subjects with TEAEs and the number of TEAEs will be summarized for the following categories:

- TEAEs (overall, serious, leading to discontinuation, and leading to death) by treatment
- TEAEs by severity and treatment
- Treatment-related TEAEs (overall, serious, leading to discontinuation, and leading to death) by treatment
- Treatment-related TEAEs by severity and treatment

The frequency of subjects will be summarized separately for TEAEs and treatment-related TEAEs by the following:

- System organ class, preferred term, and treatment
- Preferred term and treatment
- System organ class, preferred term, day of onset, and treatment (Part B only)

For the AE data the following rules will apply:

- For the derivation of TEAE status: If the start date/time of an AE is incomplete or missing, an AE will be assumed to be a TEAE, unless the incomplete start date/time or the end date/time indicates an AE started prior to dosing (Part A) or the first dose (Part B).
- For the derivation of treatment-related TEAE status: If the study treatment relationship for a TEAE is missing, a TEAE will be assumed to be a treatment-related TEAE.

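### Part A pools placebo over capsaicin-challenged and unchallenged groups, so the placebo column is a like-for-like control for no dose level in the all-TEAE tables

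*SAP*

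**What the plan says.** Section 6.1, Table 1 gives Part A a single placebo column for Groups A1 to A11, with the footnote "Placebo will be pooled across all groups". Each OLP-1002 dose level is one group.

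Section 8.6 limits the challenge to some groups: "Capsaicin intradermal test will be performed for subjects in Groups A2, A4, A6, A9, A10 and A11". Each of those subjects attends a pre-screening test and is then "tested twice during the study (1 predose and 1 postdose"), so one injection falls after study drug.

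Section 4.1 fixes the allocation. For the groups without the challenge: "Groups A1, A3, A5, A7, and A8 will consist of 4 subjects; 3 subjects will receive OLP-1002 and 1 subject will receive placebo". For the groups with it: "Groups A2, A4, A6, A9, A10, and A11 will consist of 8 subjects; 6 subjects will receive OLP-1002 and 2 subjects will receive placebo".

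Section 8.7.1 defines a TEAE as "an AE that starts during or after dosing (Part A"), with the matching rule for Part B and for events that worsen after dosing. TEAEs are summarised by treatment. Nothing in the SAP splits a safety table by capsaicin status, sets procedure-related events apart in the TEAE tables, or names the issue as a limitation.

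**The concern.** A pooled placebo column in an ascending-dose study is sound when placebo subjects are handled alike in every cohort. Here they are not: 12 undergo a painful procedure inside the treatment-emergent window and 5 do not. If that procedure produces recorded adverse events, the placebo rate is a blend that no dose level shares. Unchallenged doses would then look safer than placebo, and challenged doses less safe, without any drug effect.

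Incidence and severity of adverse events is a primary endpoint (Section 3.1). No inferential safety analysis is planned (Section 8.7.8), so what the reader concludes comes directly from comparing columns.

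A second, separate matter is the order of the doses. The 12 and 20 µg groups (A7, A8) are unchallenged and the 40, 80 and 160 µg groups (A9 to A11) are all challenged. A procedure effect would therefore first show, relative to the two doses just below, at the top of the range.

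**Working it through.** **Reproducing the plan's total.** Section 4.1 says: "Overall, 68 healthy subjects will be studied in 11 groups". Five groups of 4 and six groups of 8 give 5×4 + 6×8 = 68, which agrees.

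**Composition by capsaicin status** (Sections 4.1, 6.1 and 8.6):

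| | Groups | Dose levels | Active | Placebo |
|---|---|---|---|---|
| Challenged | A2, A4, A6, A9, A10, A11 | 120 ng; 1.2, 6, 40, 80, 160 µg | 6×6 = 36 | 6×2 = 12 |
| Unchallenged | A1, A3, A5, A7, A8 | 30 ng; 400 ng; 3, 12, 20 µg | 5×3 = 15 | 5×1 = 5 |

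Pooled placebo is 12 + 5 = 17 subjects. The challenged share is 12/17 = 70.6% and the unchallenged share is 5/17 = 29.4%. Every active column is 100% or 0% challenged.

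**Expected shift with no drug effect.** Let b be the background TEAE risk and c the absolute risk of a recorded TEAE added by the postdose injection.

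- Pooled placebo: b + (12/17)c
- Challenged dose minus pooled placebo: (b + c) − (b + 0.706c) = +0.294c
- Unchallenged dose minus pooled placebo: b − (b + 0.706c) = −0.706c
- Challenged dose minus unchallenged dose: c

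The background risk b cancels from all three differences. The SAP does not give c, so a range is assumed:

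| Assumed c | Challenged dose vs pooled placebo | Unchallenged dose vs pooled placebo | Challenged vs unchallenged dose |
|---|---|---|---|
| 0 | 0 | 0 | 0 |
| 0.10 | +2.9 points | −7.1 points | 10 points |
| 0.30 | +8.8 points | −21.2 points | 30 points |
| 0.50 | +14.7 points | −35.3 points | 50 points |

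**After splitting placebo.** Challenged active and challenged placebo both have risk b + c. Unchallenged active and unchallenged placebo both have risk b. The expected difference within each stratum is 0. The last column of the table above does not change, because it compares active groups and placebo does not enter it.

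**If A9 to A11 are not run** (Table 1 marks them as included if required). Placebo is then 6 challenged and 5 unchallenged, so 6/11 = 54.5% are challenged. The shifts become +0.455c and −0.545c, and the mismatch remains.

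**The case against.** The strongest objection is that the SAP does not establish that c is above zero. Section 8.7.1 classifies events already recorded as adverse events. It does not say that expected capsaicin reactions are recorded as such. Sections 8.6.1 and 8.6.2 capture the pain and hyperalgesia as pharmacodynamic data. Section 8.7.6 turns study-drug injection-site findings into adverse events only at Grade 3 or above, or with ulceration. That rule does not cover capsaicin, but it shows that not every expected local reaction in this study becomes an adverse event. Recording rules may sit in the protocol, which was not available. This stands, and it is why the range starts at 0.

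The shift is also small against the resolution of one cohort. One event is 1/6 = 16.7 points in a challenged dose group and 1/3 = 33.3 points in an unchallenged one. Over the assumed range the challenged shift stays below one event, and the unchallenged shift passes one event only when c exceeds 0.333/0.706 = 0.47. This stands for any single dose level. However, the shift has the same sign at every dose level in a stratum, so it does not average out down the table.

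Partial safeguards exist. Treatment-related TEAEs are tabulated separately, and dose escalation rests on group-by-group review of blinded data (Section 9), not on the final pooled column. The all-TEAE tables have no such safeguard. In the related tables, possibly related events count, and a missing relationship is taken as related.

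A reader might infer three stronger claims that the SAP does not support:

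- **Pooling creates a false step between 20 and 40 µg.** That step compares two active groups. It comes from the design and is the same however placebo is displayed.
- **Every safety contrast is biased in a known direction.** The direction is known only if c is above 0, and no mechanism is evident for laboratory, ECG or study-drug injection-site data.
- **Vital signs and heat pain are distorted.** That depends on whether an assessment falls soon after the challenge, and the SAP gives no such schedule. Heat pain is tested on the thigh, capsaicin is injected in the forearm, and VAS pain is followed for 5 minutes or until it returns to 0.

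**Conclusion.** The point holds for the all-TEAE summaries. The pooled Part A placebo column, 12 of 17 challenged, is a like-for-like control for no dose level. With no drug effect, the expected distortion is +0.29c for challenged doses (0 to 15 points) and −0.71c for unchallenged doses (0 to 35 points), for c assumed between 0 and 0.50. The composition follows from the SAP's planned allocation; the size rests wholly on the assumed c.

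The confounding of capsaicin status with dose between A8 and A9 is real but is a feature of the design. Splitting placebo does not remove it, so it needs reading within stratum and a stated limitation. Because the safety analysis is descriptive, the risk is a misread table, not an inflated error rate. The capsaicin pharmacodynamic summaries are unaffected, since only challenged groups contribute to them. This is an inexpensive improvement to a primary safety display, not a flaw that invalidates the analysis.

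**What to change.** - In the Part A TEAE tables, show placebo in two columns, capsaicin groups (n=12) and non-capsaicin groups (n=5), beside the pooled column. Do the same in any other safety table with a timepoint after the capsaicin injection.
- Compare each dose level with its matching placebo column, and read trends across doses within capsaicin stratum.
- State in the SAP and the study report that capsaicin status changes together with dose between 20 µg and 40 µg, and that splitting placebo does not resolve this. Note also that only the challenged groups attended a capsaicin pre-screening visit.
- Where the data identify adverse events attributed to the capsaicin procedure, repeat the TEAE summary without them. The SAP does not mention such a field, so this is conditional.

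The cost is limited to SAP wording and table shells before database lock; the split columns need no new data. The price is precision. One event in the n=5 column is 1/5 = 20 points, and in the n=12 column 1/12 = 8.3 points, against 1/17 = 5.9 points when pooled. The pooled column is kept for that reason. Both columns are above the n<3 threshold below which Section 8.1.1 withholds most summary statistics for continuous data.
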